10.1 Data confidentiality

Participant data from the Qualtrics survey will include a cell phone number as an identifier and address for participants who self-enrolled via the study poster and are interested in receiving a firearm storage device shipped to their address. The data will be transferred and then stored, managed, and analyzed on a secure, encrypted server behind the University of Pennsylvania Health System (UPHS) firewall. All study personnel that will use this data are listed on the IRB application and have completed training in HIPAA standards and the CITI human subjects research. Data access will be password protected. Whenever possible, data will be de-identified for analysis. Computer-based files will only be made available to personnel involved in the study through the use of access privileges and passwords. Wherever feasible, identifiers will be removed from study-related information. Precautions are already in place to ensure the data are secure by using passwords and HIPAA-compliant encryption.

Participant cell phone numbers will be used for the distribution of the Amazon gift card and sharing the link to the follow-up survey. The gift card will be distributed via text using the Nudge Unit's Google Voice account.

The Qualtrics response will be monitored daily and is placed in a folder in a UPHS secure shared drive. Access is granted only for staff with HIPAA and CITI training. The file created is saved onto a secure UPHS drive only accessible by the team on this protocol (via password protection) or using the Penn Secure Share encrypted document sharing mechanism. There will be no individual demographic information collected. Qualtrics tracked data includes time and location of survey completion. This information will not be used as part of the study except for ensuring there aren't imposter participants with completion rates that are outside the daily average cable lock distribution at PAH. The dataset will remain on this secure shared drive until the project is complete. It will be removed at the end of that initiative, unless a separate protocol request for access to this dataset is approved by the IRB before it is removed.

Every effort will be taken by the research staff to protect patient confidentiality by keeping this information on a secure UPHS shared drive (which requires institutional privileges and manual approval by administrators for access). The file will be password protected.

10.2 Subject confidentiality

The only personal information collected will only be their cell phone number and shipping address in the case of participants enrolling via the study poster. Any information that is obtained will be used for research purposes only. All study staff will be reminded of the confidential nature of the data collected and contained in these databases. All study personnel that will use this data are listed on the IRB application and have completed training in HIPAA standards and the CITI human subjects research. Data access will be password protected. Whenever possible, data will be de-identified for analysis. The only identifier in the file will be their cell phone number and will remain on the secure shared drive for the purposes of distributing compensation in the form of digital gift cards.

10.3 Subject privacy

All efforts will be made by study staff to ensure subject privacy. Data will be evaluated in a de-identified manner whenever possible.

10.4 Data disclosure

Information on individual participants will not be disclosed to anyone outside of the study team.

10.5 Data safety and monitoring

The investigators will provide oversight for the study evaluation of this study. All unanticipated problems or adverse events will be reported to the primary PI for the duration of the study. The PI is responsible for identifying potential unanticipated problems experienced by study participants, adjusting the intervention accordingly and reporting the experience to the IRB.

10.6 Risk/benefit

10.6.1 Potential study risks

The potential risks associated with this study are minimal given the research is focused on testing data collection methodologies in a low-profile and non-threatening way. Breach of data is a potential risk that will be mitigated by using HIPAA compliant and secure data platforms for analysis as previously described.

10.6.2 Potential study benefits

The main potential benefit is development of critical evidence to facilitate the scaling of this program to our hospitals and launch a promising research program to study the acceptability, long term use, and cost-effectiveness of a scalable approach to promote safe firearm storage. Study participants may benefit from receiving a firearm storage device as a result. However, it is possible that participants will receive no benefit from this study.

16. 9. wptrace. Missing Pieces. The Trace. Published November 20, 2017. Accessed June 1, 2023. <https://www.thetrace.org/2017/11/stolen-guns-violent-crime-america/>
18. 10. Grossman DC, Mueller BA, Riedy C, et al. Gun storage practices and risk of youth suicide and unintentional

Brief Description for ClinicalTrials.gov

This study aims to enhance workplace safety by implementing a firearm safety program at Penn Medicine's Pennsylvania Hospital. The option to store firearms securely during visits is offered to firearm

owners. The study focuses on understanding barriers and facilitators to this program and piloting methods to collect data on firearm storage device use. The approach prioritizes participant confidentiality and pragmatism. The study design involves iterative pilot testing of data collection methods and comparison of acceptance and usage rates between cable locks and lock boxes through randomization. The intended outcome is to provide evidence supporting the scalability and effectiveness of the program. The study population includes patients and visitors who accept firearm safety materials or express interest in receiving a firearm storage device. The primary outcome measure is survey response rate, with secondary outcomes including firearm storage behavior and likelihood of using a gun safety device. Additionally, the study explores variations in survey distribution methods.

Detailed Description for ClinicalTrials.gov

To prevent workplace violence, in November 2021, Penn Medicine implemented the Evolv weapons detection system in Pennsylvania Hospital (1,2). For individuals who self-disclose they are carrying a weapon, or who are identified with weapon during screening, security guards offer the individual the option to leave with their weapon, or to place it in a safe, at the hospital, for storage. Security guards return the weapon when the patient or visitor is ready to leave. Beginning in July 2022 our team piloted a program in which security guards offer a cable lock and safety brochure when the gun owner returns to retrieve their firearm at the conclusion of their visit. To date, 47% of patients and visitors who stored their firearm with security have taken a cable lock when offered, resulting in over 400 firearm safety locks and brochures distributed to firearm owners. The Aims of this study are to: (1) Elucidate barriers and facilitators to implementing a hospital security screening firearm safety program through interviews with hospital security staff; (2) Design and pilot test a method for collecting data on storage device use among patients and visitors who accept firearm safety materials; (3) Conduct a pilot of distributing lockboxes and compare acceptance and usage rates to cable locks.

This protocol is for Aim 2 and 3 of the study. The rationale for this aim is that traditional research methods for collecting data on firearm safe storage have not been optimized for use in a pragmatic setting to ensure acceptability and confidentiality. Our priority in firearm safety education and device distribution is to get the necessary information and supplies to those who need them. To achieve this, any data collection must be done in a low profile, confidential, and non-threatening way. This is particularly important not only because discussions of firearm ownership can be politically charged, but also because some community members may not be legally licensed to own or carry a firearm, and some may even be legally prohibited from doing so. The legal status of their ownership does not lessen their need for safety information and support—indeed, unlicensed firearm owners may have even fewer safety resources available for them. Our priority is therefore to reach as many individuals as possible while subjecting them to as little scrutiny as possible. Therefore, we aim to design a data collection approach that will prioritize preserving participant confidentiality. Our approach will be iterative pilot tests of data collection methods including embedding unique QR codes linked to surveys in firearm safety brochures and study poster signage. We will offer the opportunity for individuals to take home a cable lock after their visit or to scan the QR code on the brochure/poster to fill out the study survey and get a safety

device shipped to their address. Participants who fill out the study survey will be randomized to receive either a cable lock as the default or a choice between cable lock and lock box to test acceptance and usage rates. For those who accepted a cable lock at the hospital will automatically be grouped in the cable lock default group. The hypothesis we are testing is if iterative pilot testing will reveal a feasible method that balances pragmatism and confidentiality as well as compare acceptance and usage rates among cable locks and lock boxes.

The intended outcome of this study is development of critical evidence to facilitate the scaling of this program to our hospitals and launch a promising research program to study the acceptability, long term use, and cost-effectiveness of a scalable approach to promote safe firearm storage.

This research study is to design and pilot test a method for collecting data on storage device use among patients and visitors who accept firearm safety materials or are interested in receiving a firearm storage device shipped to their address. The study design is an iterative pilot test of survey data collection methods and determination of scalability and feasibility for distribution of firearm storage devices. The study population and sample will be (a) individuals who are patients or visitors to PAH who are screened for a firearm, screen positive, and accept a firearm safety brochure and storage device OR (b) individuals interested in receiving a firearm storage device and self-scan the unique QR code on the study poster in the entry hall of PAH with minimal or no security supervisor engagement. A unique QR code linking directly to the initial survey will be embedded into the firearm safety brochure as well as the poster in the entry hall of PAH next to the distribution area. Individual group (a) will be informed by security that survey participation is optional, but that it is helpful for our efforts, and that participation will be compensated with a \$10 Amazon gift card for the initial survey and a \$20 Amazon gift card for completing the follow-up survey. Individual group (b) will not be actively engaged by security, and will self-enroll in the study by viewing the posted signage and completing the QR code linked survey. Individuals who decline the device will also be eligible for the initial survey via the poster QR code, but they will not be eligible for the follow-up survey.

The primary outcome measure is survey response rate: whether an eligible visitor or patient completed the firearm storage survey after accepting firearm safety materials or after scanning the QR code on the poster. This will be measured through Qualtrics survey completion rate and PAH Evolv security system foot traffic. We will use the survey completion rate as the numerator and the number of people scanning positive for a firearm as the denominator for this rate.

The secondary outcome measures are from initial and follow-up survey responses: (1) firearm storage behavior, (2) likelihood of using gun safety device within the next week (extremely unlikely to extremely likely scale). These outcomes are directly tied to questions asked in both surveys.

Lastly, as exploratory outcomes, we will compare survey response rates between several different variations of survey distribution: web survey accessed via QR code posted in the entry hall; web survey accessed via QR code included on the safety brochure; follow-up survey link administered by text message.

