This protocol is for Aim 2 of the study. The rationale for this aim is that traditional research methods for collecting data on firearm safe storage have not been optimized for use in a pragmatic setting to ensure acceptability and confidentiality. Our priority in firearm safety education and device distribution is to get the necessary information and supplies to those who need them. To achieve this, any data collection must be done in a low profile, confidential, and non-threatening way. This is particularly important not only because discussions of firearm ownership can be politically charged, but also because some community members may not be legally licensed to own or carry a firearm, and some may even be legally prohibited from doing so. The legal status of their ownership does not lessen their need for safety information and support—indeed, unlicensed firearm owners may have even fewer safety resources available for them. Our priority is therefore to reach as many individuals as possible while subjecting them to as little scrutiny as possible. Therefore, we aim to design a data collection approach that will prioritize preserving participant confidentiality. Our approach will be iterative pilot tests of data collection methods including embedding unique QR codes linked to surveys in firearm safety brochures and study poster signage. The hypothesis we are testing is if iterative pilot testing will reveal a feasible method that balances pragmatism and confidentiality.

The intended outcome of this study is development of critical evidence to facilitate the scaling of this program to our hospitals and launch a promising research program to study the acceptability, long term use, and cost-effectiveness of a scalable approach to promote safe firearm storage.

2. Overall objectives

Paralleling national trends during the Covid-19 pandemic, in 2021 in Philadelphia, there was a 600% increase in new firearm licenses, resulting in a large increase in new firearm owners (16). Effectively promoting secure storage of firearms among new and pre-existing owners could have a major impact on injury prevention, but existing educational and legislative means have had limited impact on promoting safe storage.

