5.1 Design

Aim 2 of this research study is to design and pilot test a method for collecting data on storage device use among patients and visitors who accept firearm safety materials or are interested in receiving a firearm storage device shipped to their address. The study design is an iterative pilot test of survey data collection methods and determination of scalability and feasibility for distribution of firearm storage devices. The study population and sample will be (a) individuals who are patients or visitors to PAH who are screened

for a firearm, screen positive, and accept a firearm safety brochure and storage device OR (b) individuals interested in receiving a firearm storage device and self-scan the unique QR code on the study poster in the entry hall of PAH with minimal or no security supervisor engagement. A unique QR code linking directly to the initial survey will be embedded into the firearm safety brochure as well as the poster in the entry hall of PAH next to the distribution area. Individual group (a) will be informed by security that survey participation is optional, but that it is helpful for our efforts, and that participation will be compensated with a \$10 Amazon gift card for the initial survey and a \$20 Amazon gift card for completing the follow-up survey. Individual group (b) will not be actively engaged by security, and will self-enroll in the study by viewing the posted signage and completing the QR code linked survey. Individuals who decline the device will also be eligible for the initial survey via the poster QR code, but they will not be eligible for the follow-up survey.

The primary outcome measure is survey response rate: whether an eligible visitor or patient completed the firearm storage survey after accepting firearm safety materials or after scanning the QR code on the poster. This will be measured through Qualtrics survey completion rate and PAH Evolv security system foot traffic. We will use the survey completion rate as the numerator and the number of people scanning positive for a firearm as the denominator for this rate.

The secondary outcome measures are from initial and follow-up survey responses: (1) firearm storage behavior, (2) likelihood of using cable lock within the next week (extremely unlikely to extremely likely scale). These outcomes are directly tied to questions asked in both surveys.

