5.2 Study duration

The aim of this study is expected to take 8 months including planning, 6-month active phase of the study, and then analysis and dissemination of results.

Activity	Month 1	Month 2	Month 3	Month 4	Month 5	Month 6	Month 7	Month 8	Month 9	Month 10	Month 11	Month 12
Aim 1												
IRB approval	Blue											
Data collection & analysis		Blue	Blue									
Manuscript				Blue	Blue							
Aim 2												
IRB approval	Green											
Initial design	Green											
Iterative data collection		Green	Green	Green	Green	Green						
Aim 3												
Lockbox vendor contract					Yellow	Yellow	Yellow					
IRB approval								Yellow				
Direct lockbox distribution									Yellow			
Lockbox voucher distribution										Yellow		
Lockbox shipping distribution										Yellow		
Analysis, manuscript, network dissemination											Yellow	

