5.6 Key exclusion criteria

None.

6. Subject recruitment

Since this aim is a trial of data collection methods within an existing hospital program, individuals will not be recruited or enrolled individually, but instead eligible individuals will be offered the option to participate in the survey upon receipt of firearm safety materials or self-selection via scanning the QR code linked to the initial study survey. The former option will be presented to individuals alongside the existing distribution workflow of the program.

7. Subject compensation

Total potential compensation per participant is \$30 in the form of Amazon gift cards. Individuals will receive a \$10 Amazon gift card for completing the initial survey. If participants choose to complete the follow-up survey, they will receive a \$20 Amazon gift card. The gift card will be shared manually via text message with the participants within 1-2 weeks of survey completion. Participants who elect to have a firearm storage device shipped to their address will receive a free device (either a cable lock and/or lock box).

8. Study procedures

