 - i. [LOGIC] Which of the following storage devices would you prefer?
 1. Lock box
 2. Trigger lock
 3. Gun safe
 4. Calmshell / "life jacket"
 5. Gun cabinet
 6. In-vehicle lock
 7. Other/key/PIN/biometric (please specify):
 - c. Don't want to share my address
 - i. [LOGIC] Please select which of the following you'd be open to:
 1. Returning to Penn Medicine to pick up a free cable lock
 2. Receiving a free cable lock locally
 3. Other (please specify)
5. [IF YES #3] What is the best US shipping address for you?
 - a. [Text box fields for street, apt, city, zip, name]
6. How do you usually store your firearm?
 - a. In a locked safe or gun cabinet
 - b. With a trigger lock or cable lock
 - c. Unlocked (not secured with a lock, in a locked container, or not stored in a locked cabinet)
 - d. Other (please specify)
7. Once you receive your cable lock, how likely are you to use it in the next week?
 - a. Extremely likely

- b. Somewhat likely
- c. Neither likely nor unlikely
- d. Somewhat unlikely
- e. Extremely unlikely

Follow-up Survey: Participants who complete the initial survey and who agree to provide contact information will be contacted via text message 1 month after enrollment for a follow-up survey that adds questions about if and how participants have changed their storage behavior. The text language will read:

“Hello, this is Penn Medicine. Thank you for completing our initial survey. If you’re interested in taking the follow-up survey, please click the survey link below: [INSERT LINK]”

Participants will receive the second Amazon gift card incentive 1-2 weeks after completion of this survey. “Hello, this is Penn Medicine. Thank you for participating in our survey. As an appreciation for your time, please see below for your gift card information: [INSERT GIFT CARD #]”

The follow-up survey questions are subject to be amended based on the principal investigators’ discretion. Eligible participants from the initial survey, those who answered yes to accepting a cable lock, will be asked the following questions to understand if their behavior changed:

1. Since you’ve visited Penn Medicine, how have you stored your firearm? [option selection]
 - a. Participants select [a] in a locked safe or gun cabinet, b) with a trigger lock or cable lock, c) unlocked (not secured with a lock, in a locked container, or not stored in a locked cabinet), d) other (please specify) with an open comment box]

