2. Have you used the firearm storage device from Penn Medicine to secure your firearm? [Yes/No]
3. Have you made any other changes in your firearm storage? [write in]

Iterative Analysis and Refinement of Data Collection Methods: We will assess response rates every (1) week and tabulate responses on the acceptability of data collection methods. We will iteratively refine data collection methods over the course of 6 months to achieve the highest possible response rate. The participant data collected will be their phone number and/or their address for individuals completed the survey via the study poster. No identifying information or demographics will be collected to uphold anonymity. Cell phone number will be used to distribute the gift card via the Nudge Unit’s Google Voice account and re-contact with invitation to participate in the follow-up survey. Their address will only be used to ship the firearm storage device to individuals who self-enrolled in the study via the study posters.

9. Analysis plan

The primary outcome is survey response rate. This will be monitored via Qualtrics by looking at response volume by week. These responses will be compared to security department reports on the number of firearms identified/stored to allow us to calculate the proportion of eligible individuals who responded per week. The secondary outcome measures are: (1) firearm storage behavior among a) locked safe/gun cabinet, b) trigger lock or cable lock, c) unsecured, d) other (write in), (2) likelihood of using cable lock within the next week (extremely unlikely to extremely likely scale).

10. Human research protection

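### The protocol body describes an Aim 2 survey pilot without arms, the registry descriptions at its end describe a randomised device comparison, and the timeline, allocation, follow-up and outcome list do not support that comparison as written

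*Protocol*

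**What the plan says.** - **Scope in the body.** Section 1: "This protocol is for Aim 2 of the study". Section 5.1: "The study design is an iterative pilot test of survey data collection methods and determination of scalability and feasibility". Section 4 mentions randomised trials only as a long-term goal. Sections 8.2 and 9 contain no allocation and no comparison of devices.
- **Scope in the registry text.** The Detailed Description for ClinicalTrials.gov says "This protocol is for Aim 2 and 3 of the study", and then "Participants who fill out the study survey will be randomized to receive either a cable lock as the default or a choice" of cable lock or lock box, with acceptance and usage as the purpose. Its next sentence puts people who accepted a cable lock at the hospital straight into the default group. The Brief Description also announces a randomised comparison of the two devices.
- **Timing.** The Section 5.2 chart has Aim 2 data collection in months 2-6. The Aim 3 rows run from "Lockbox vendor contract" (months 5-7) through a separate IRB approval (month 8) to lock-box distribution (months 9-10). The text of 5.2 gives 8 months in total with a 6-month active phase. Section 7, however, says a shipped device may be "either a cable lock and/or lock box".
- **Address.** Only the poster survey asks for one. Section 8.2: "Their address will only be used to ship the firearm storage device to individuals who self-enrolled in the study via the study posters". Sections 10.1 and 10.2 say the same in substance.
- **Follow-up.** Section 8.2 describes the eligible participants as "those who answered yes to accepting a cable lock". Section 5.5 is wider and also admits poster respondents who want a device shipped.
- **Outcomes.** Both the body and the registry text list survey response rate as primary, and storage behaviour and likelihood of use as secondary. The likelihood item concerns a cable lock in the body and a gun safety device in the registry text.

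**The concern.** These are two designs in one current document. A reader of the registry entry would expect a randomised comparison of a cable-lock default with a choice that includes a lock box. Someone running the study from Sections 5, 8 and 9 would not randomise anyone.

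If the comparison is attempted on the text as it stands, three things are at risk. The two options may not be available at the same time. One arm mixes randomised and non-randomised people. Some of those randomised are never asked whether they used a device. Any of these would leave a difference between arms that randomisation does not protect.

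**Working it through.** The protocol gives no sample size or power figure for this comparison, so there is none to reproduce. The check sets the sections side by side, with simple arithmetic.

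**1. Timing (Section 5.2 chart; one-month follow-up from Section 8.2).**
- Last charted enrolment is month 6, so the last follow-up is 6 + 1 = month 7.
- First lock-box distribution is month 9, which is 9 - 7 = 2 months after the last follow-up and 9 - 8 = 1 month beyond the stated duration.
- The chart shades five collection months against a stated active phase of six. If six months are counted from month 2, enrolment ends in month 7 and follow-up in month 8, still before month 9.
- Section 7 allows a lock box to be shipped without any such delay, so the body is not consistent with itself on availability.

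**2. Automatic grouping (registry Detailed Description).** Let q be the share of survey completers who already took a cable lock at the hospital, with the rest randomised 1:1.
- Default group = q + (1 - q)/2. Choice group = (1 - q)/2.
- Non-randomised share of the default group = q / [q + (1 - q)/2] = 2q/(1 + q).
- The documents do not give q. The nearest figure is the 47% of people storing a firearm who took a lock when offered. With q = 0.47, the default group is 0.735 and the choice group 0.265 of completers, a ratio of 2.77:1. The non-randomised share is 0.47/0.735 = 64%.
- The share rises with q. More poster self-enrollers without a lock would lower it; more brochure respondents with a lock would raise it.

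If the true use rate is the same, p, in both randomised arms and is a among the automatically grouped, the apparent difference (choice minus default) is (p - a) × 2q/(1 + q). With p = 50% and q = 0.47:
- a = 30%: 50% - (0.47 × 30% + 0.265 × 50%)/0.735 = +12.8 points.
- a = 50%: 0 points.
- a = 80%: 50% - (0.47 × 80% + 0.265 × 50%)/0.735 = -19.2 points.

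The use rates are assumptions chosen to show the range. The sign is not known in advance.

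**3. Brochure route (Sections 5.5 and 8.2 against the registry text).**
- Took a cable lock: grouped automatically, so not randomised; eligible for follow-up.
- Took no cable lock: could be randomised, but has no address item for shipment and is not eligible for follow-up under 5.5 or 8.2.
- Nobody on this route is therefore both randomised and followed.

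**4. Poster route.** There is an address item. Under 5.5, anyone wanting a shipped device is followed; under 8.2, only cable-lock acceptors are. The two sections give different answers for a person who chooses a lock box.

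**5. Outcomes.** The registry text gives acceptance and usage as the purpose of randomising, but neither outcome list names them. Follow-up item 2 asks about use of the supplied device without naming its type, so use can be measured in those followed. Storage behaviour is a listed outcome and could be tabulated by arm. No survey item records which device a willing respondent chose, and the poster likelihood item names only a cable lock.

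**The case against.** The registry text looks later than the body: it cites over 400 locks distributed where the body cites over 300. On that reading the chart belongs to a narrower Aim 2 plan, and the randomised phase need not fall in months 2-6. The surveys are expressly open to refinement, so an address or device item could be added. This is fair, but the registry text is part of the current document and not a change log. Rewording a survey does not settle scope, allocation or when lock boxes exist.

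Several stronger readings are tempting and should not be made:
- *Everyone who completes a survey is randomised.* The registry text exempts people who took a cable lock at the hospital. For the same reason, the missing address item matters only for brochure respondents without a lock.
- *A lock-box chooser is never followed.* Section 8.2 reads that way, but 5.5 admits poster respondents wanting any shipped device. This is a conflict between sections.
- *There is no outcome to compare, or the comparison cannot be run.* Storage behaviour and follow-up item 2 could both be compared by arm. Section 7 also allows lock boxes to be shipped.
- *The primary outcome is useless because it precedes randomisation.* It serves Aim 2, and no section proposes comparing it between device arms.
- *Later lock-box data will be set against earlier cable-lock data.* No section plans this. It is a risk to guard against if the chart is followed.

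**Conclusion.** The contradiction on aims and randomisation is established by the text alone and needs no assumption. So are the chart's gap between survey collection and lock-box distribution, its conflict with Section 7, the unrandomised entry into the default arm, the conflict between 5.5 and 8.2, and the absence of acceptance and use from the outcome lists.

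The supportable conclusion is that the randomised comparison is not supported as written. A reader might infer that it is impossible, but the documents do not show that.

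The 64% non-randomised share rests on q = 0.47 and 1:1 allocation, neither of which is stated for survey completers. The range of +12.8 to -19.2 points adds assumed use rates. These figures illustrate the size of the problem; the conclusion does not depend on them. It should be fixed, because it decides whether any device difference can be read as a randomised result.

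**What to change.** State one scope throughout.

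**If the randomisation stays:**
- Describe it in Sections 5.1, 8.2 and 9.
- Compare only people randomised concurrently while both devices are available, analysed as randomised. Report the automatically grouped cable-lock takers separately.
- Reconcile the Section 5.2 chart with Section 7 on when lock boxes can be supplied.
- Add an address item to the brochure survey for respondents without a lock, and amend the address-use statements in 8.2, 10.1 and 10.2 to match.
- Align 8.2 with 5.5 so that everyone randomised and sent any device is followed, including those on the brochure route.
- List device acceptance and follow-up item 2 (used, yes/no) as outcomes by arm, and record which device was offered and taken.

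**If it does not stay:** delete the randomisation and the cable-lock versus lock-box comparison from the registry text, and restore the Aim 2 scope there.

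**Cost.** Either way, an amendment or text correction and a matching registry update. Keeping the randomisation has a further cost: the device comparison can use only respondents enrolled once lock boxes are available. On the present chart that is after the survey phase and past the 8 months, so the chart and duration must be restated and earlier respondents do not count towards it. It also means collecting addresses from more people, in a study that puts confidentiality first. Deletion has neither of these costs.
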